Copper IUD	Yes	xx	xx	x.xx (x.xx, x.xx)	x.xx (x.xx, x.xx)
	No	xx	xx	1.00 (Reference)	1.00 (Reference)
Type 3 group test for interaction with breastfeeding status					P = 0.xxxx

CI = confidence interval; HR = hazard ratio; IUD = intrauterine device; LNG-IUD = levonorgestrel-releasing intrauterine system.

Note: Crude HRs were estimated from the Cox model including breastfeeding status, IUD type, and their interaction. Adjusted HRs were estimated from the Cox models including breastfeeding status, IDU type, and their interaction, weighted using overlap weights.

Generated using xxxx.sas on xxxxxxx.

Table Layout 12.2. Effect Modification of IUD Type on Postpartum Status and Uterine Perforation;
Analysis Set: Complete Study Population, First IUD Insertion;
Database: Pooled

Modifier IUD Type	Exposure Postpartum Status	Number of Events	Number of Insertions	Crude HR (95% CI)	Adjusted HR (95% CI)
LNG-IUD	6 weeks or less	XX	XX	x.xx (x.xx, x.xx)	x.xx (x.xx, x.xx)
	> 6 to ≤ 14 weeks	XX	XX	x.xx (x.xx, x.xx)	x.xx (x.xx, x.xx)
	> 14 to ≤ 52 weeks	XX	XX	x.xx (x.xx, x.xx)	x.xx (x.xx, x.xx)
	> 52 weeks or no delivery	XX	XX	1.00 (Reference)	1.00 (Reference)
Copper IUD	6 weeks or less	XX	XX	x.xx (x.xx, x.xx)	x.xx (x.xx, x.xx)
	> 6 to ≤ 14 weeks	XX	XX	x.xx (x.xx, x.xx)	x.xx (x.xx, x.xx)
	> 14 to ≤ 52 weeks	XX	XX	x.xx (x.xx, x.xx)	x.xx (x.xx, x.xx)
	> 52 weeks or no delivery	XX	XX	1.00 (Reference)	1.00 (Reference)
Type 3 group test for interaction with postpartum status					P = 0.xxxx

CI = confidence interval; HR = hazard ratio; IUD = intrauterine device; LNG-IUD = levonorgestrel-releasing intrauterine system.

Note: Crude HRs were estimated from the Cox model including postpartum status, IUD type, and their interaction. Adjusted HRs were estimated from the Cox models including postpartum status, IDU type, and their interaction, weighted using overlap weights.

Generated using xxxx.sas on xxxxxxx.

**Table Layout 13. Percentage of Uterine Perforation or IUD Expulsion Before and After Implementation of ICD-10-CM Coding;
 Analysis Set: Complete Study Population, First IUD Insertion;
 Database: Pooled and by Site**

Site	1-Year Before			1-Year After		
	Patients N	Uterine Perforation n (%)	IUD Expulsion n (%)	Patients N	Uterine Perforation n (%)	IUD Expulsion n (%)
Pooled	xx	xx (xx.x)	xx (xx.x)	xx	xx (xx.x)	xx (xx.x)
KPNC	xx	xx (xx.x)	xx (xx.x)	xx	xx (xx.x)	xx (xx.x)
KPSC	xx	xx (xx.x)	xx (xx.x)	xx	xx (xx.x)	xx (xx.x)
KPWA	xx	xx (xx.x)	xx (xx.x)	xx	xx (xx.x)	xx (xx.x)
RI	xx	xx (xx.x)	xx (xx.x)	xx	xx (xx.x)	xx (xx.x)

[figure not shown]
IUD = intrauterine device.

Generated using xxxx.sas on xxxxxxxx.

[figure not shown]
Programming note 1: Research partners will provide counts for this table.

9.6 Illustration of Continuous Enrollment and Look-Back Time for Kaiser Permanente Sites (KPNC, KPSC, and KPWA)

[figure not shown]
Scenario 1. One IUD Insertion With No Uterine Perforation or IUD Expulsion

Scenario 2. One IUD Insertion With One Uterine Perforation

Scenario 3. Two IUD Insertions, With One IUD Expulsion and One Perforation

Note: if the beginning date of the study period is within the continuous enrollment period (illustrated in the above figures), the beginning date of the study period will be used as the beginning of continuous enrollment. Similarly, if the end date of the study period is within the continuous enrollment period, the end date of the study period will be used as the end of the continuous enrollment.

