4.9 Data analysis

Descriptive analyses for all variables of interest will be presented overall and stratified by database.* For categorical variables, frequencies and percentages will be presented for each level. For continuous variables, the mean, standard deviation, minimum, maximum, median, and quartiles will be presented. For estimates, two-sided 95% confidence intervals will be calculated.

* Descriptive and comparative analyses for all variables of interest will be presented overall and stratified by database, with the exception of IUD type. The variable IUD type will be analyzed by database, but only each database holder and RTI-HS will have access to the database-specific information. Data shared with Bayer will only present IUD type aggregated over all data sources. Additionally, analyses for objectives 18 and 26 will be presented by database only if there are more than 20,000 subsequent IUD insertions for the research partner that can be included in the analysis.

Crude incidence rates and cumulative incidence of the outcomes will be estimated for each exposure group (i.e., postpartum IUD insertion time category, breastfeeding status at the time of IUD insertion, type of IUD [LNG vs. copper]).

Crude hazard ratios will be calculated for each outcome without adjustment for covariates within each database. Confounding adjustment will be performed via overlap weighting. Adjusted hazard ratios will be calculated accounting for the propensity score-based weighting approach.

Effect estimates across all data sources will be estimated and presented as the main study results. Effect estimates, except IUD type, will also be presented for each database.

Analyses of the adjusted hazard ratios for the two primary objectives (uterine perforation by breastfeeding status at IUD insertion and uterine perforation by postpartum timing of IUD insertion [in four categories]) combined across all data sources will include hypothesis testing using two-sided statistical tests with a significance level of 0.05 (as requested by the FDA) to test the hypothesis of no difference in the perforation risk between the exposed and referent groups. There will be no adjustment for multiplicity. Statistical tests will be conducted on the assumption that residual confounding can be neglected. However, the validity of this assumption cannot be assessed within the framework of this study.

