8.1 Primary objective

The primary objectives in this study are as follows:

1. To evaluate whether the risk of uterine perforation among women who were breastfeeding at the time of first observed IUD insertion differs from the risk of uterine perforation among women who were not breastfeeding at the time of first observed IUD insertion
2. To evaluate whether the risk of uterine perforation among women who had a first observed IUD insertion within different time periods postpartum (i.e., ≤ 6 weeks, > 6 weeks and ≤ 14 weeks, > 14 weeks and ≤ 52 weeks) differs from the risk of uterine perforation among women who had their first observed IUD insertion more than 52 weeks postpartum, including women without a recorded delivery within the past 52 weeks

Both primary objectives will include modification by the data source (i.e., interaction terms) if preliminary testing indicates statistically significant interaction between data source and breastfeeding (objective 1) or timing of postpartum insertion (objective 2). Interaction terms for data source will be included only for the objective(s) with statistically significant interaction(s).

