9.7.3 Study objective–specific data analysis

9.7.3.1 Analyses of primary objectives

In order to address the primary objectives 1 and 2 in Section 8.2, the primary endpoints in the study are the adjusted hazard ratios for uterine perforation among the following groups of women (Table 7):

1. Women who were breastfeeding at the time of first observed IUD insertion versus those who were not breastfeeding at the time of first observed IUD insertion.
2. Women who had a first observed IUD insertion within different time periods postpartum (i.e., ≤ 6 weeks, > 6 weeks and ≤ 14 weeks, > 14 weeks and ≤ 52 weeks) versus those who had a first observed IUD insertion late in the postpartum period (more than 52 weeks postpartum, including those without recorded delivery in the past 52 weeks).

Table 7. Study cohorts relevant primary objectives

Objective number	Brief description	Complete study population	Breastfeeding status available	IUD type available
1	By breastfeeding status		X	
2	By postpartum category	X		

IUD = intrauterine device.

Adjusted hazard ratios will be developed for each group of women as described in Section 9.7.1.3.3. Additionally, the interaction effect between the data source and the exposure will be assessed after confounding adjustment. The interaction will be assessed by including terms for exposure, database, and the interaction between the database and the exposure in the weighted Cox models. A type 3 group test for the interaction terms will be conducted. If the test is statistically significant ($P < 0.05$), then the interaction terms will be retained in the final model, and the adjusted hazard ratios will be reported for each data source. If the interaction terms are not deemed significant, then the interaction terms will be removed, and the overall adjusted hazard ratios (the main effect) will be reported as the results of the primary analyses.

Two-sided 95% CIs of the adjusted hazard ratios for uterine perforation will be presented, and a two-sided overall test of the null hypothesis that the natural logarithm of the adjusted hazard ratio equals to 0 will be performed for each of the primary objectives.

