6.2.1 Analysis for Primary Objectives

In the following groups of women, the adjusted hazard ratios for uterine perforation will be evaluated:

- Objective 1. Women who were breastfeeding at the time of the first observed IUD insertion versus those who were not breastfeeding at the time of the first observed IUD insertion.
- Objective 2. Women who had a first observed IUD insertion within different time periods postpartum (i.e., ≤ 6 weeks, > 6 weeks and ≤ 14 weeks, > 14 weeks and ≤ 52 weeks) versus those who had a first observed IUD insertion late in the postpartum period (more than 52 weeks postpartum, including those without recorded delivery in the past 52 weeks).

For objective 1, analyses will be conducted using Analysis Set 2 (breastfeeding status is available). For objective 2, analyses will be conducted using Analysis Set 1 (complete study population). Both analyses will use only the first observed IUD insertion.

Cox regression models will be used to obtain crude hazard ratios overall and by data source with assessment of the proportional hazards assumption (Section 4.1.4).

Confounding effects will be adjusted using the propensity score weighting method (Section 4.1.5). After developing the propensity score model, calculating the weights, and assessing the balance between exposure groups in the weighted sample, adjusted hazard ratios will be estimated using the weighted Cox regression model as described in Section 4.1.6. Additionally, the interaction effect between the data source and the exposure will be assessed after adjustment for confounding. The interaction will be assessed by including terms for exposure, database, and the interaction between the database and the exposure in the weighted Cox models. A type 3 group test for the interaction terms will be conducted. If the test is statistically significant ($P < 0.05$), then the interaction terms will be retained in the final model, and the adjusted hazard ratios will be reported for each data source. If the interaction terms are not statistically significant, then the interaction terms will be removed, and the overall adjusted hazard ratios (the main effect) will be reported as the results of the primary analyses.

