Two-sided 95% CIs of the adjusted hazard ratios for uterine perforation will be presented overall or by data source, as appropriate. If the exposure-by-data source interaction is not significant, then the corresponding two-sided test of the null hypothesis that the natural logarithm of the overall adjusted hazard ratio equals 0 will be performed. The significance level of 0.05 will be applied. There will be no adjustment for multiplicity.

As a sensitivity analysis, confounding effects will be accounted for by including selected key covariates in the unweighted Cox models. The Cox models will include exposure, site, exposure-by-site interaction, and baseline covariates. Due to the sparse outcomes, limited covariates will be selected for inclusion based on their association with the study outcome. The sensitivity analysis will be conducted only for the primary objectives.

Planned Analysis Tables 1.1 (for breastfeeding status) and 2.1 (for postpartum status) will present crude hazard ratio and hazard ratio adjusted via overlap weighting. Analysis Tables 1.2.1 through 1.3.5 and 2.2.1 through 2.3.5 will present baseline characteristics by exposure and standardized differences (described in Section 4.1.5) prior to and after overlap weighting. Analysis Tables 1.4 and 2.4 will present hazard ratios adjusted by including baseline covariates in the model. Results related to the development of propensity score models will be presented in Analysis Tables 33.1.1, 33.2.1, 33.2.2, 33.3.1, 33.3.2 and Analysis Figures 33.1.1 and 33.1.2.

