Programming note 4: Site (data source) will be shown only for the pooled table, not for the site tables.

Programming note 5: Results by IUD type will be presented only for the pooled table, not by site.

**Table Layout 2.1. Hazard Ratios of Uterine Perforation for Breastfeeding Status;
 Analysis Set: Breastfeeding Status Available, First IUD Insertion;
 Database: Pooled and by Site**

Site	Breastfeeding Status	Events	Insertions	Person-years	Crude HR (95% CI)	Adjusted	
						HR (95% CI)	P Value
Pooled	Yes	XX	XX	XXX,XXX.X	x.xx (x.xx, x.xx)	x.xx (x.xx, x.xx)	0.XXXX
	No	XX	XX	XXX,XXX.X	1.00 (Reference)	1.00 (Reference)	-
KPNC	Yes	XX	XX	XXX,XXX.X	x.xx (x.xx, x.xx)	x.xx (x.xx, x.xx)	0.XXXX
	No	XX	XX	XXX,XXX.X	1.00 (Reference)	1.00 (Reference)	-
KPSC	Yes	XX	XX	XXX,XXX.X	x.xx (x.xx, x.xx)	x.xx (x.xx, x.xx)	0.XXXX
	No	XX	XX	XXX,XXX.X	1.00 (Reference)	1.00 (Reference)	-
KPWA	Yes	XX	XX	XXX,XXX.X	x.xx (x.xx, x.xx)	x.xx (x.xx, x.xx)	0.XXXX
	No	XX	XX	XXX,XXX.X	1.00 (Reference)	1.00 (Reference)	-
RI	Yes	XX	XX	XXX,XXX.X	x.xx (x.xx, x.xx)	x.xx (x.xx, x.xx)	0.XXXX
	No	XX	XX	XXX,XXX.X	1.00 (Reference)	1.00 (Reference)	-

CI = confidence interval; HR = hazard ratio; IUD = intrauterine device.

Note: Crude HRs were estimated from five Cox models using pooled data or within each site. Adjusted HRs were estimated from two Cox models weighted using overlap weights. The adjusted HRs by site were estimated from the Cox model including exposure, site, and site-by-exposure interaction (type 3 group test for interaction: $P = 0.xxxx$); the overall adjusted HR (reported only if the interaction is not significant) was estimated from the Cox model including exposure and site.

Note: The P value is from the Cox model for the test of the null hypothesis that the adjusted HR equals one.

Note: The proportional hazards assumption was tested using the global correlation test based on Schoenfeld residuals with the pooled data ($P = 0.xxxx$).

Generated using `xxxx.sas` on `xxxxxxx`.

Programming note 1: The pooled adjusted HR and related footnote will be shown only if the interaction term is not statistically significant ($P > 0.05$).

Programming note 2: If the proportional hazards assumption is violated, time-dependent exposure covariates will be included in Cox models. The table above will be expanded to include separate hazard ratios for the effect of exposure over time.

Programming note 3: For tables that include results by IUD type, only pooled results will be presented, not by site.

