Note: Crude HRs were estimated from five Cox models using pooled data or within each site. Adjusted HRs were estimated from two Cox models weighted using overlap weights: The adjusted HRs by site were estimated from the Cox model including exposure, site, and site-by-exposure interaction (type 3 group test for interaction: $P = 0.xxxx$); the pooled adjusted HR (reported only if the interaction is not significant) was estimated from the Cox model including exposure and site.

Note: The P value is from the Cox model for the test of the null hypothesis that the adjusted HR equals one.

Note: The proportional hazards assumption was tested using the global correlation test based on Schoenfeld residuals with the pooled data ($P = 0.xxxx$).

Generated using xxxx.sas on xxxxxxx.

Programming note 1: The pooled adjusted HR and related footnote will be shown only if the interaction term is not significant ($P > 0.05$).

Programming note 2: For tables that include results by IUD type, only pooled results will be presented, not by site.

Table Layout 3.1. Baseline Characteristics and Absolute Standardized Differences of Baseline Characteristics for Breastfeeding Status;
Analysis Set: Breastfeeding Status Available, First IUD Insertion;
Database: Pooled

Characteristic	Breastfeeding Status		Absolute Standardized Difference
	Yes (N = XX,XXX)	No (N = XX,XXX)	
Age, in years			
Category, n (%)			
Category 1	xx (x.x)	xx (x.x)	xx.x
Category 2	xx (x.x)	xx (x.x)	xx.x
Category 3	xx (x.x)	xx (x.x)	xx.x
N	xx	xx	
Mean (SD)	xx.x (x.xx)	xx.x (x.xx)	xx.x
Median [Q1, Q3]	xx.x [xx.x, xx.x]	xx.x [xx.x, xx.x]	
Min, max	xx, xx	xx, xx	
Continue for other variables under consideration			

IUD = intrauterine device; Q1 = 25th percentile; Q3 = 75th percentile; SD = standard deviation.

Generated using xxxx.sas on xxxxxxxx.

Programming note 1: For tables that include results by IUD type, only pooled results will be presented, not by site.

**Table Layout 3.2. Baseline Characteristics and Absolute Standardized Differences of Baseline Characteristics for Postpartum Status;
 Analysis Set: Complete Study Population, First IUD Insertion;
 Database: Pooled**

Characteristic	Postpartum Status				Absolute Standardized Difference (vs. > 52 Weeks or No Delivery)			
	6 Weeks or less (N = XX)	> 6 to ≤ 14 Weeks (N = XX)	> 14 to ≤ 52 Weeks (N = XX)	> 52 Weeks or No Delivery (N = XX)	6 Weeks or Less	> 6 to ≤ 14 Weeks	> 14 to ≤ 52 Weeks	Maximum Difference
Age, in years								
Category, n (%)								

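### The overall adjusted hazard ratio and its test for both primary objectives are reported only if a site-by-exposure test is not significant; that test's statistic is unstated, and at the planning inputs it often trips falsely for objective 2

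*SAP*

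**What the plan says.** SAP 6.2.1 fits a weighted Cox model with exposure, database and their interaction, and then: "A type 3 group test for the interaction terms will be conducted". If P < 0.05 the terms stay and adjusted HRs are reported by data source. The overall test is conditional: "If the exposure-by-data source interaction is not significant, then the corresponding two-sided test of the null hypothesis that the natural logarithm" of the overall adjusted HR is zero is performed. SAP 9.5 repeats the condition for the tables: "The pooled adjusted HR and related footnote will be shown only if the interaction term is not statistically significant" (Layout 2.1, Programming note 1) and "The pooled adjusted HR and related footnote will be shown only if the interaction term is not significant" (Layout 2.2). The footnotes of both layouts say the same.

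The Protocol is not of one mind. Section 4.9 says: "Effect estimates across all data sources will be estimated and presented as the main study results". It places the primary tests on adjusted HRs "combined across all data sources will include hypothesis testing using two-sided statistical tests with a significance level of 0.05 (as requested by the FDA". Section 9.7.3.1 has a retain-or-remove rule on the same interaction test, but also says without condition that an overall test will be done for each primary objective. Sections 4.3.1 and 8.1 say only that interaction terms are added: "Both primary objectives will include modification by the data source (i.e., interaction terms) if preliminary testing indicates statistically significant interaction".

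SAP 4.1.6 names the sandwich variance for 95% CIs only. SAP 6 lets the study team combine, exclude or leave alone any cell with a count below 10, deciding when such cells are found.

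**The concern.** A preliminary test decides whether the primary result exists. If it trips, the single pooled adjusted HR and P value on which the power in Protocol Table 4 rests are not reported. The gate has 9 degrees of freedom for objective 2 and 3 for objective 1. It is applied to a rare outcome across four sites of very unequal size, so empty site-by-exposure cells are expected. Whether it trips can then depend on the statistic the analyst takes from the software and on a sparse-cell choice made after outcome counts are known.

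**Working it through.** **Inputs.** Protocol 9.5: perforation risk 1.3 per 1,000; 225,000 insertions at 5:20:5:70 (objective 2); 60,000 at 60:40 (objective 1). Protocol 9.4.1 to 9.4.4: about 100,000, 80,000, 15,000 and 5,700 insertions with 12 months' history, which sum to 200,700. Site shares are therefore KPNC 49.8%, KPSC 39.9%, KPWA 7.5% and RI 2.8%. Three of these counts are given as lower limits. Assumed: the same allocation and the same true HR at every site, so that every rejection by the gate is false.

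**The plan's own figures.** Schoenfeld power is Φ(ln HR × √(D p(1−p)) − 1.96), with D events and exposed share p.
- Objective 1, HR 2.0: D = 60,000 × 0.0013 = 78, p = 0.6. Φ(0.693 × √18.72 − 1.96) = Φ(1.04) = 85%.
- ≤ 6 weeks, HR 2.0: D = 168,750 × 0.0013 = 219.4, p = 5/75. Φ(0.693 × √13.65 − 1.96) = Φ(0.60) = 73%.

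Both match Table 4.

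**Power left at one site.** With D multiplied by the site share, power at HR 2.0 (objective 1 / ≤ 6 weeks) is KPNC 56/44%, KPSC 47/37%, KPWA 13/10% and RI 7/6%.

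**Expected events, objective 2, HR 1** (292.5 × site share × allocation):

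| Site | ≤ 6 wk | 6–14 wk | 14–52 wk | > 52 wk |
|---|---|---|---|---|
| KPNC | 7.3 | 29.1 | 7.3 | 102 |
| KPSC | 5.8 | 23.3 | 5.8 | 81.6 |
| KPWA | 1.1 | 4.4 | 1.1 | 15.3 |
| RI | 0.42 | 1.66 | 0.42 | 5.8 |

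Eleven of 16 cells expect fewer than 10 events. The chance of at least one empty cell is 1 − ∏(1 − e^(−m)) over the cell means m, which is 96%. At HR 2 with the overall risk held at 1.3 per 1,000 it is about 87%.

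**Why the statistics misbehave.**
- Robust Wald: in an empty cell the coefficient runs off towards minus infinity, while that cell adds almost nothing to the sandwich variance. The test rejects almost whenever a cell is empty, and rarely otherwise.
- Model-based Wald and weighted likelihood ratio: weights are treated as counts. Without confounding, the normalised overlap weight in category k is 1/(4e_k), with e_k the category's share: 5, 1.25, 5 and 0.36. One ≤ 6-week event counts as five.

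**False-trip rates** (simulation, Poisson form of the weighted Cox likelihood, 5% level, HR 1 / HR 2):

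| Scenario | Robust Wald | Weighted LR | Model-based Wald |
|---|---|---|---|
| Objective 2, cells left alone | 96/87% | 82/78% | 28/30% |
| Same, 4× the events (assumed) | 38/18% | 75/71% | 54/60% |
| Objective 2, KPWA and RI excluded | 3.4/3.7% | 42/40% | 40/39% |
| Objective 1, cells left alone | 54/66% | 8/8% | 1/1% |

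Rates move by a few points between runs; for objective 1 the robust Wald rate lay between about 51% and 70%. A robust score test for objective 2 gave 45/34%. Full-data weighted Cox fits on 225,000 women (197 replicates per HR) gave 98/87%, 81/80% and 22/30% for the first row. An unweighted likelihood-ratio test, all four sites kept, rejected in about 5–7% for both objectives.

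**The case against.** Four counter-arguments deserve weight.

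1. *The percentages are a worst case.* Largely right. The risk of 1.3 per 1,000 is a 1-year figure, and follow-up has no maximum, so more events are likely. Robust Wald then falls sharply, and excluding KPWA and RI brings it to about 3.5%. A reader might infer that 28–96% is a general error range for the gate. The documents do not support that: it spans different statistics at one event count under one of three permitted sparse-cell options. What stands is that more events do not rescue the two tests that treat weights as counts. Excluding the two small sites leaves those tests near 40%, and drops RI, which was added for generalizability (Protocol 4.3 footnote).

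2. *IUD type (objective 16) is safe.* A reader might infer that a tripped gate leaves objective 16 with no reportable adjusted HR, since Programming note 1 hides the pooled value and note 3 the site values. But SAP 9.1 (footnote b), the objective 16 entry in SAP 9.4 and the note below that table all require pooled-only reporting for IUD type. The notes conflict and need a clarifying word; the result is not lost.

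3. *The Protocol does not suppress the pooled HR.* Correct for 4.3.1 and 8.1, which only add interaction terms. The explicit suppression is in the SAP.

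4. *Other results remain.* True: the crude pooled HR, the site-specific adjusted HRs, and the pooled analyses of objectives 17, 28, 29 and 31. None is the overall adjusted HR that the primary objectives call for.

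It is also fair that a pooled HR is less informative when sites truly differ. That argues for showing site HRs beside it, not for withholding it.

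**Conclusion.** The point holds. SAP 6.2.1 and Layouts 2.1 and 2.2 conflict with Protocol 4.9 and with the overall-test sentence of Protocol 9.7.3.1, and the passages must be reconciled whatever the gate's error rate. Even a correctly sized gate would withhold each overall result in 5% of studies with no site differences.

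As written, the rate for objective 2 can be far higher: about 28% to 96% at HR 1, depending on the statistic, at the 1-year event count with cells left alone. At HR 2 the pooled result would survive in about 13% (robust Wald) to 70% (model-based Wald) of studies. For objective 1 the inflation is serious only for robust Wald.

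These sizes rest on the site shares, allocation and common HR assumed above. The objective 1 shares are the least certain: KPSC breastfeeding data start two years after its EHR data (Protocol Table 3), and the KPWA mother-infant file is described as current only through 2015 (Protocol 9.4.3).

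**What to change.** - Always report the pooled adjusted HR, 95% CI and P value (weighted Cox model with exposure and site, robust variance) as the primary result for objectives 1 and 2.
- Delete the condition in SAP 6.2.1 and in Programming note 1 and the footnotes of Layouts 2.1 and 2.2.
- Align the retain-or-remove sentence in Protocol 9.7.3.1 with its overall-test sentence and with 4.9. Sections 4.3.1 and 8.1 need at most a phrase saying that the pooled result is still reported.
- Keep the interaction P value and site-specific adjusted HRs as supportive results. Where a site has a zero-event cell, show the counts and mark the HR not estimable.
- State the interaction statistic in advance. A likelihood-ratio test in the unweighted, covariate-adjusted model already planned in SAP 6.2.1 and Layout 7 is a suitable option, with false rejection of about 5–7%. It tests a conditional HR with fewer covariates. Once the pooled result is always shown, this choice no longer threatens it.
- For objective 16, say that Programming note 1 does not apply.

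The cost is wording, with no extra data. Under true heterogeneity the pooled HR is an average, with the site HRs beside it. The FDA asked for the database-interaction assessment (Protocol 5, amendment 1) and approved the protocol (SAP 1.2), so the change should be cleared with the agency; the assessment itself is kept.
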